## **The importance of physical activity in HF**

The inability to perform exercise or physical activity without discomfort may be one of the first symptoms experienced by patients with HF and is a principal reason for seeking medical care. Heart failure is a major health problem, with an increasing incidence and a gloomy prognosis that is typically accompanied by an increasing limited capacity for physical activity and worsening overall HR-QoL (Wielenga 1997).

Physical inactivity alone is a serious problem and has been identified as the fourth leading risk factor for global mortality causing an estimated 3.2 million deaths worldwide (Caspersen 1985, Steele 2000).

In multiple studies of HF patients, a reduction in physical activity as measured by actigraphy has been demonstrated to be strongly predictive of both mortality and hospitalization (Howell 2010). A study of actigraphy data collected from onboard accelerometers in implanted cardioverter defibrillators (ICDs) found physical activity to be a strong predictor of outcome in a large cohort of HF patients (Conraads 2014). In addition, a recent study of 60 New York Heart Association (NYHA) III HF patients identified the specific activity pattern features of skewness (a measure of the symmetry of the distribution curve) and kurtosis (a measure of the sharpness of the peak of the distribution curve) to be independently predictive of all-cause mortality (Melin 2016). On the other hand, an increase in capacity for physical activity has been shown to be beneficial for HF patients. Exercise induced improvement in capacity for activity results in a significant improvement in all parameters of quality of life including physical, psychological, social and environmental domains (Bocalini 2008).

[figure not shown]

Figure 2 Kaplan-Meier estimates for the incidence of death or hospitalization. 834 patients stratified in 4 groups based on the combination of physical activity and the CHARM risk score. For both parameters, the median value (188 min/d and 4.8 points, respectively) is used to group patients in the low or high category. (Conraads 2014)

## **Actigraphy to assess impact of HF management on physical activity**

To date, only one study has used actigraphy to assess treatment effects in HF patients. A study of the effect of isosorbide mononitrate on the activity levels of HF patients with preserved ejection fraction used actigraphy to assess effects on subjects' movement levels over 6 weeks (Redfield 2015). While there was no significant between-group difference in 6 MWT, or QoL questionnaire results (KCCQ, Minnesota living with heart failure), actigraphy data revealed a dose-dependent trend toward lower activity levels and a statistically significant decrease in active time per day in subjects in the highest dose treatment arm. Although the reduction of activity levels in the treatment group was unexpected, this study further demonstrated the sensitivity of objective assessments in comparison to traditional questionnaire-based approaches. It is noteworthy that there were significant technical limitations in the device used in this study that may have contributed to the seemingly paradoxical results. The activity sensor used in this study compiled and stored data in 15 minute epochs; while this has no impact on the measurement of overall activity, grouping activity data into epochs this length reduced the

resolution of the activity data, and limits opportunities for the assessment of activity patterns. Other actigraphy studies of patients with chronic illness have demonstrated that more symptomatic patients have generally both a reduction in activity when active and are less still when resting, compared to healthier patients (Maurer 2009). If HF patients spend most of their time at rest, treatment related increases in physical activity when active may be offset by a concomitant reduction in movement when at rest. As a result, this can appear as a simple decrease in overall activity if accelerometry data is compiled and averaged over large periods of time (when long measurement epochs are used).

### **Sleep and HF**

Sleep is the companion HR-QOL function to physical activity, and is equally important as it fills the portion of the day not available for physical activity. Multiple studies of sleep dysfunction in heart failure patients have demonstrated an inextricable association between sleep function, mortality, and sleep-disordered breathing (Penzel 2015). Other studies also suggest that sleep apnea may lead to the progression of cardiac dysfunction in HF patients (Berman 1991). The adverse effect on cardiac function probably arises from repetitive apneas causing excessive stimulation of the sympathetic nervous system, arterial oxyhemoglobin desaturation and increases in systemic blood pressure (Bradley 1996). The incidence of sleep-disordered breathing, specifically central sleep apnea, is higher in the congestive heart failure (CHF) population where it has been demonstrated to be an independent predictor of mortality (Kasai 2012, Lanfranchi 1999). There is also evidence of a complex association between ventricular arrhythmias and sleep-disordered breathing (Sin 1999) and data that suggests the observed increase in mortality is the result of increased incidence of sudden death (Yumino 2009, Kasai 2012). In addition, the discontinuity of sleep by frequent arousals may also lead to the development of excessive daytime sleepiness and fatigue in CHF patients with sleep apneas (Hanly 1995). In HF patients, poor sleep quality and continuity was correlated with reduced daytime activity, self-reported physical function, and mental health (Redeker 2005).

## **1.2 Purpose**

The purpose of this study is to investigate the effects of initiation of sacubitril/valsartan vs enalapril treatment on objective measures of both waking activity and sleep in subjects with heart failure with reduced ejection fraction.

## **2 Study objectives and endpoints**

[figure not shown]
Measurements will be done at weeks -1, 1, 8, 9, and 16. Week 8 is considered the primary time point (end of double blind period).

[figure not shown]
## 2.1 Objectives and related endpoints

**Table 2-1 Objectives and related endpoints**

Objective(s)	Endpoint(s)
Primary Objective(s) 

The primary objective is to evaluate the effect of initiation of sacubitril/valsartan treatment versus enalapril on physical activity during the waking hours as an objective measure of physical function.

	Endpoint(s) for primary objective(s) 

The primary endpoint is the change in mean activity counts collected during the most active 30 minutes of the subject's day between baseline phase (mean of data collected each day during week -1) and the final randomized treatment phase measurement (mean of endpoint data collected each day during week 8), as measured by wrist-worn accelerometer collected actigraphy (total counts per 30 min period collected during the most active 30 minutes of each day).

Secondary Objective(s) 

The secondary objective is to evaluate the effect of initiation of sacubitril/valsartan treatment versus enalapril on subjects' sleep as an objective measure of physical function.

	Endpoint(s) for secondary objective(s) 
The secondary endpoints include:
 

Change in mean activity (counts per minute) during sleep between baseline phase (mean of data collected during week -1) and the final randomized treatment phase measurement (mean of data collected during week 8), as measured by actigraphy (activity counts per minute during daily sleep period, wrist-worn accelerometer).

The change in mean activity during sleep between baseline phase (mean of data collected during the nights of week -1) and each randomized treatment and open label phase measurement, as measured by actigraphy (Week 1, 9, and 16) (activity counts per minute during daily sleep period, wrist-worn accelerometer).

The change in mean activity counts collected during the most active 30 minutes of the subject's day between

Objective(s)	Endpoint(s)
	baseline phase (mean of data collected each day during week -1) and each randomized treatment and open label phase measurement (Week 1, 9, and 16), as measured by wrist worn accelerometer collected actigraphy.

### **3        Investigational plan**

[figure not shown]
#### **3.1      Study design**

This study is a multicenter, randomized, double-blind, double dummy, parallel group, active-controlled 8-week study with open label extension using medical device-grade subject worn sensors to measure waking and sleeping physical activity in the ambulatory outpatient setting. The 18 week study duration will consist of a 2-week baseline observation phase (with subjects continuing their current heart failure drug therapy), followed by an 8 week blinded treatment phase during which subjects are randomized (1:1) to either initiation of sacubitril/valsartan treatment or enalapril comparator, and finally an 8 week open label extension phase during which all subjects are treated with sacubitril/valsartan. Each subject will undergo a 36 hour washout period [during which ACEi (Angiotensin converting enzyme inhibitor), or study drug will be withheld] before the start of the randomized, blinded treatment phase, and again before beginning the open label extension phase. The study will include 8 office visits and 5 tele-visits.

Subjects will wear a wrist-worn actigraphy device continuously for the 18 week duration of the study, from the time of enrollment (the start of the 2 week baseline phase) to the end of the open-label extension phase (end of treatment week 16). During this 18 week interval, the devices will be exchanged five times during five study visits, to guard against data loss and ensure adequate battery life. Data will be collected continuously during the trial and although only data collected during assessment periods will contribute to prospectively defined endpoints, other data may be assessed in future analysis of patterns observed during the study. Additionally, continuous wear reduces opportunities for lapses in compliance while adding very minimal assessment burden for subjects.

Each assessment period is seven contiguous days. This will allow for continuous actigraphy recording over the seven day period.

**Figure 3-1** Study design

### 3.2 Rationale for study design

The design of the study facilitates the assessment of change in sequential daily physical activity, [REDACTED] HF symptoms and health-related quality of life; between baseline to select time point assessment periods after randomized, blinded assignment to treatment with sacubitril/valsartan versus the active comparator enalapril. Assessment of the primary endpoint at 8 weeks captures the early impact of initiation of sacubitril/valsartan versus enalapril, which is the focus of the study.

Waking activity will be the primary endpoint, and sleep activity (a measure of sleep disturbance) is the secondary endpoint. Actigraphy, which has been well characterized for the measurement of both daytime and sleep physical activity variables, will be used to inform the primary and secondary endpoints.

[figure not shown]
Prior to randomization, there will be a 2 week phase where device familiarization and baseline assessment will be completed. The initial baseline week will provide an opportunity for the subjects to become familiar and acclimated to the testing devices and assessment routines, prior to entering the baseline phase of the study. Data from the second week of this phase, the 'baseline phase' (Week -1) will be considered as the baseline value for comparison to subsequent periods. Data collected outside of the defined measurement periods will be excluded from analysis for the defined study endpoints.

The 36-hour wash-out interval after randomization and before entering the open-label extension is required per the FDA approved USPI label because there is a potential for increased risk for angioedema in subjects who receive both an ACE inhibitor and the combination of sacubitril/valsartan.

The randomized comparison phase of 8 weeks provides the direct assessment of the initial and early changes associated with sacubitril/valsartan treatment to treatment with the active comparator enalapril.

The open label phase of 8 weeks provides the opportunity for every subject to receive sacubitril /valsartan. This results in one group of subjects that will receive sacubitril/valsartan for a total of 16 weeks, providing information on the endpoints after this duration of continuous therapy. It also provides the opportunity to evaluate changes after initiating sacubitril/valsartan in a group of subjects who all had been previously receiving enalapril treatment for 8 weeks.

The subject population will be described in more detail in the [Section 4](#) below.

### **3.4 Rationale for choice of comparator**

Treatment with ACEi has been well established as the standard of care for renin-angiotensin-aldosterone system (RAAS) blockade and is recommended by treatment guidelines as a 1A recommendation for all subjects with CHF and reduced left ventricular ejection fraction (LVEF), unless ACEi-intolerant. Additionally, ACEi may reduce aortic stiffness by opposing vasoconstrictive, hypertrophic, and profibrotic effects of angiotensin II on the vessel wall.

### **3.5 Purpose and timing of interim analyses/design adaptations**

Not applicable.

### **3.6 Risks and benefits**

The risk to subjects in this trial will be minimized by compliance with the eligibility criteria and study procedures, close clinical monitoring, and the provision of rescue options.

Experience in the PARADIGM-HF trial; both in the run-in phase as well as the double-blind randomization phase indicated that the major risks associated with the treatment of sacubitril/valsartan are renal dysfunction, hyperkalemia, and hypotension. Results from the TITRATION study indicated that subjects whom are ACEi or ARB naïve are at an increased risk of experiencing these adverse events.

In this study, the risk of experiencing renal dysfunction, hyperkalemia, and hypotension are mitigated in this study by appropriate up-titration of the drug at weeks 2, 4, 8, 10, and 12. The risks are further mitigated by appropriate inclusion and exclusion criteria. Subjects are excluded if they have a potassium > 5.2 mmol/l at screening.

Sacubitril/valsartan may also cause angioedema. The risk of developing angioedema is increased if subjects take both an ACEi and sacubitril/valsartan. To decrease this risk, all subjects will undergo a 36 hour wash out period before entering the randomized phase epoch and before continuing into the open-label treatment epoch to minimize the interaction between an ACEi and sacubitril/valsartan in potentiating the development of angioedema.

All subjects will be allowed to continue receiving the rest of their background cardiovascular (CV) medications throughout the study. Subjects will be randomized to study treatment only after the investigator has confirmed the subject is on stable treatment with guideline-directed therapy for heart failure with reduced ejection fraction (HFrEF), other than ACEis and ARBs, which will ensure that subjects are receiving appropriate treatment for their heart failure.

In the PARADIGM-HF study, sacubitril/valsartan reduced the risk of cardiovascular (CV) death, HF hospitalization and due to these significant results, sacubitril/valsartan is now indicated to reduce these risks in subjects with chronic heart failure (NYHA class II-IV) and reduced ejection fraction.

## **4 Population**

The study population will consist of outpatient male and female subjects, between 18 - 80 years of age, with HFrEF NYHA class II or III. The goal is to have a total of approximately 136 subjects randomized, in approximately 25-30 centers in the United States. Subjects must meet all inclusion and none of the exclusion criteria.

### **4.1 Inclusion criteria**

Subjects eligible for inclusion in this study must fulfill all of the following criteria:

1. Written informed consent must be obtained before any assessment is performed.
2. Men and women between 18 and 80 years of age
3. Subjects diagnosed with NYHA class II or III heart failure and with reduced ejection (HFrEF) (Reduced ejection is defined as left ventricular EF  $\leq$  40%. LVEF  $\leq$  40% may be determined via any local measurement within the past 6 months prior to signing consent, using echocardiography, multi gated acquisition scan (MUGA), CT scanning, MRI or ventricular angiography provided no subsequent study documenting an EF of  $>$ 40%. If the EF measurement is expressed as a value range, the average of the range endpoint values should be used as the EF).
4. Subjects must be a candidate for treatment with sacubitril/valsartan as per USPI
5. Subjects must be living in a traditional residence, apartment, or non-communal adult home where they can move about freely and frequently and are primarily responsible for scheduling their sleep and daily activities

#### **4.2 Exclusion criteria**

Subjects fulfilling any of the following criteria are not eligible for inclusion in this study. No additional exclusions may be applied by the investigator, in order to ensure that the study population will be representative of all eligible subjects.

1. Subjects with a history of hypersensitivity to any of the study drugs, including history of hypersensitivity to drugs of similar chemical classes, or allergy to ACEIs, ARBs, or NEP inhibitors as well as known or suspected contraindications to the study drugs.
2. Subjects with a history of angioedema drug related or otherwise
3. Subjects with symptomatic hypotension or systolic blood pressure  $<$ 100 mmHg at screening or  $<$ 95 mmHg at randomization.
4. Subjects with any conditions in skin or upper extremities which would limit the ability to tolerate a wrist-worn actigraphy device on the nondominant arm for 24 hours/day for the duration of the study.
5. Subjects unwilling or unable to wear and operate the study measurement devices for the phases required.
6. Subjects who are currently hospitalized, or were discharged from the hospital within 4 weeks prior to enrollment.
7. Subjects who are already taking sacubitril/valsartan
8. Subjects who are nonambulatory or use mobility assistive devices such as motorized devices, wheelchairs, or walkers. The use of canes for stability while ambulating is acceptable.
9. Subjects with physical activity impairment primarily due to conditions other than heart failure such as:
  - Exertional angina
  - inflammatory or degenerative joint disease
  - gout
  - peripheral vascular disease

- neurologic diseases affecting activity or mobility

10. Subjects with nontypical circadian behavioral patterns (for example: shift workers actively rotating shifts, subjects with non-24-hour sleep wake disorder as result of blindness)

11. Subjects with tremor, rigor or mobility limitations affecting the nondominant arm (e.g. due to Parkinson's disease, joint contractures, paralysis, injury etc.)

12. Subjects with chronic obstructive pulmonary disease (COPD) who require supplemental oxygen.

13. Subjects using a continuous positive airway pressure (CPAP) devices or similar technology for treatment of sleep disorders

14. Subjects unwilling or unable to refrain from the use of prescription and/or over the counter (OTC) sleep aids for the duration of the study

15. Subjects with body mass index (BMI) > 35

16. Subjects with chronic persistent atrial fibrillation.

17. Subjects with diabetes who are taking aliskiren.

18. Subjects receiving nesiritide

19. Subjects taking bile acid sequestering agents such as cholestyramine or colestipol (to avoid interference with study drug absorption).

20. Subjects who are enrolled or participating as a subject in any other clinical trial involving any investigational agent or investigational device within 30 days before screening.

21. Subjects with a potassium > 5.2 mEq/L at screening.

22. Subject with a history of malignancy of any organ system who have a life expectancy of less than 1 year.

23. Pregnant or nursing (lactating) women, where pregnancy is defined as the state of a female after conception and until the termination of gestation, confirmed by a positive human chorionic gonadotropin (hCG) laboratory test.

24. Women of child-bearing potential, defined as all women physiologically capable of becoming pregnant, unless they are using highly effective methods of contraception during dosing and for 7 days after stopping of study medication. Highly effective contraception methods include:

- a. Total abstinence (when this is in line with the preferred and usual lifestyle of the subject). Periodic abstinence (e.g., calendar, ovulation, symptothermal, post-ovulation methods) and withdrawal are not acceptable methods of contraception
- b. Female sterilization (have had surgical bilateral oophorectomy with or without hysterectomy) total hysterectomy or tubal ligation at least six weeks before taking investigational drug. In case of oophorectomy alone, only when the reproductive status of the woman has been confirmed by follow up hormone level assessment
- c. Male sterilization (at least 6 months prior to screening). For female subjects on the study, the vasectomized male partner should be the sole partner for that subject
- d. Use of oral, (estrogen and progesterone), injected or implanted hormonal methods of contraception or placement of an intrauterine device (IUD) or intrauterine system (IUS) or other forms of hormonal contraception that have comparable efficacy (failure rate <1%), for example hormone vaginal ring or transdermal hormone contraception.

In case of use of oral contraception women should have been stable on the same pill for a minimum of 3 months before taking investigational drug.

Women are considered post-menopausal and not of child bearing potential if they have had 12 months of natural (spontaneous) amenorrhea with an appropriate clinical profile (e.g. age appropriate, history of vasomotor symptoms) or have had surgical bilateral oophorectomy (with or without hysterectomy), total hysterectomy or tubal ligation at least six weeks ago. In the case of oophorectomy alone, only when the reproductive status of the woman has been confirmed by follow up hormone level assessment is she considered not of child bearing potential.

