## Glossary of terms

Cohort	A specific group of patients/subjects fulfilling certain criteria
Control drug	Drugs(s) used as a comparator to reduce assessment bias, preserve blinding of investigational drug, assess internal study validity, and/or evaluate comparative effects of the investigational drug
Dosage	Dose of the study treatment given to the patient in a time unit (e.g. 100 mg once a day, 75 mg twice a day)
Electronic Data Capture (EDC)	Electronic data capture (EDC) is the electronic acquisition of clinical study data using data collection systems, such as Web-based applications, interactive voice response systems and clinical laboratory interfaces. EDC includes the use of Electronic Case Report Forms (eCRFs) which are used to capture data transcribed from paper source forms used at the point of care.
eSource	eSource Direct Data Entry (DDE) refers to the capture of clinical study data electronically, at the point of care. eSource Platform/Applications reduce the use of paper capture source data during clinical visits. eSource combines source documents and case report forms (eCRFs) into one application, allowing for the real time collection of clinical trial information to sponsors and other oversight authorities, as appropriate.
Enrollment	Point/time of patient entry into the study at which informed consent must be obtained (e.g. prior to starting any of the procedures described in the protocol)
Epoch	A portion of the study which serves a specific purpose. Typical epochs are: screening/recruitment, wash-out, treatment, and follow-up
Investigational drug	The drug whose properties are being tested in the study; this definition is consistent with US CFR 21 Section 312.3 and is synonymous with "investigational new drug" or "investigational medicinal product."
Medication pack number	A unique identifier on the label of each investigational drug package
Part	A single component of a study which contains different objectives or populations within that single study. Common parts within a study are: a single dose part and a multiple dose part, or a part in patients/subjects with established disease and in those with newly-diagnosed disease.
Patient/subject ID	A unique number assigned to each patient upon signing the informed consent
Randomization number	A unique identifier assigned to each randomized patient, corresponding to a specific treatment arm assignment
Reduced Ejection Fraction	Left ventricular ejection fraction $\leq$ 40%

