### **5.3 Treatment assignment and randomization**

At visit 3 all eligible subjects/subjects will be randomized via Interactive Response Technology (IRT) to one of the treatment arms. The investigator or his/her delegate will contact the IRT after confirming that the subject fulfills all the inclusion/exclusion criteria. The IRT will assign a randomization number to the subject, which will be used to link the subject to a treatment arm and will specify a unique medication number for the first package of study drug to be dispensed to the subject.

The randomization numbers will be generated using the following procedure to ensure that treatment assignment is unbiased and concealed from subject and investigator staff. A subject randomization list will be produced by the IRT provider using a validated system that automates the random assignment of subject numbers to randomization numbers. These randomization numbers are linked to the different treatment arms, which in turn are linked to medication numbers. A separate medication list will be produced by or under the responsibility of Novartis Drug Supply Management using a validated system that automates the random assignment of medication numbers to packs containing the investigational drug(s).

The randomization scheme for subjects will be reviewed and approved by a member of Biometrics USCDMA.

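### The 4-week discharge look-back in exclusion 6 stops at enrollment, so a hospital stay that begins and ends during the baseline phase is not excluded and can supply the Week -1 baseline

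*Protocol*

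**What the plan says.** - **The criterion.** Protocol section 4.2, exclusion 6: "Subjects who are currently hospitalized, or were discharged from the hospital within 4 weeks prior to enrollment". It has two parts: an undated one on current hospitalization and a look-back with a date.
- **Where the look-back ends.** The protocol glossary defines enrollment as "Point/time of patient entry into the study at which informed consent must be obtained". Section 3.1 has the watch worn "from the time of enrollment (the start of the 2 week baseline phase"). Enrollment is therefore Visit 1, about two weeks before randomization at Visit 3.
- **What is checked at Visit 3.** Section 5.3: "The investigator or his/her delegate will contact the IRT after confirming that the subject fulfills all the inclusion/exclusion criteria". Section 3.6 adds: "Subjects will be randomized to study treatment only after the investigator has confirmed the subject is on stable treatment with guideline-directed therapy". The latter is not among the criteria in section 4.
- **Investigator discretion.** Section 4.2: "No additional exclusions may be applied by the investigator".
- **What the baseline is.** Section 3.2 says that Week -1 data "will be considered as the baseline value for comparison to subsequent periods".
- **What screens the baseline data.** SAP section 2.5.1 drops dates with under 8 hours of valid activity data and needs at least 5 days for a weekly mean. SAP section 2.5.3 falls back to the preceding week if Week -1 is missing or unevaluable. Protocol section 6.6.4 repeats the baseline phase for watch non-compliance. None of these rules mentions a hospital stay.

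**The concern.** The primary variable is the change in peak 30-minute activity from Week -1 to Week 8. A week in hospital, or the first week at home afterwards, would probably show depressed activity, and later recovery would then count as change. The trial keeps recently discharged patients out at entry but does not carry that condition through the two weeks in which the baseline is measured. Exclusion 3, by contrast, tests systolic pressure at screening and again "mmHg at randomization".

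Two things are at stake. The randomized comparison gains noise. And the paired t-tests at Weeks 9 and 16 in the sacubitril/valsartan arm (protocol section 9.5.1, SAP section 2.7.2) use Week -1 as baseline with no concurrent control, so recovery from a depressed baseline adds directly to the apparent improvement.

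**Working it through.** **1. Does the wording leave a gap?** Three cases:

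| Hospital stay | Look-back part | Current-hospitalization part at Visit 3 | Result |
|---|---|---|---|
| Discharge less than 4 weeks before Visit 1 | met | not met | excluded |
| Begins after Visit 1, still in hospital at Visit 3 | not met | met | excluded |
| Begins after Visit 1, discharged before Visit 3 | not met | not met | not excluded |

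A patient discharged before Visit 1 must be at least 4 weeks past discharge at Visit 1, so about 5 weeks past it when Week -1 starts and about 6 at randomization (visit windows of 3 days either way). In the third case the required interval is zero.

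**2. Does that week become the baseline?** It depends on the watch.
- *Discharged on Day -8, watch worn at home.* All of Week -1 is valid, and a just-discharged week is the baseline.
- *In hospital Day -10 to Day -4, watch worn.* Week -1 can pass the 5-day rule and stands.
- *Same stay, watch off.* Full days left are Day -14 to -11 (4 days) in Week -2 and Day -3 to -1 (3 days) in Week -1. Neither reaches 5. Either the baseline phase is repeated under section 6.6.4, or the patient drops out of the analysis under SAP section 2.5.3.
- *Repeated baseline started at discharge.* The new Week -1 falls about 8 to 14 days after discharge. Nothing says that enrollment is re-dated.

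**3. The plan's own figure.** Inputs from protocol section 9.8: difference 5000, SD 7400, two-sided 0.05, 90% power, 20% drop-out plus 10% non-evaluable. n per arm = 2 × (1.960 + 1.282)² × (7400/5000)² = 46.0, taken as 47. Then 94/0.70 = 134.3, or 135; the t-based version gives 48 per arm and 96/0.70 = 137.1, or 138. The stated 136 lies between them. In reverse, 136 × 0.70 = 95.2 evaluable, or 47.6 per arm, and power = Φ(5000/(7400 × √(2/47.6)) − 1.96) = 0.909.

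**4. How many patients?** The documents give no admission rate. Assume 0.3 to 1.0 all-cause admissions per patient-year over 14 days:
- 0.3: 1 − exp(−0.3 × 14/365.25) = 1.1%; × 136 = 1.6 patients
- 0.6: 2.3%; 3.1 patients
- 1.0: 3.8%; 5.1 patients

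These are upper bounds at each rate. They include patients still in hospital at Visit 3, stays with the watch off, and stays early in Week -2.

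**5. Effect on power.** If a share p has Week -1 lowered by D counts (assumed 5,000 to 15,000; not in the documents), the SD of change is at most about √(7400² + p(1 − p)D²), before any gain from covariate adjustment. At 47.6 per arm:

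| p | D = 5,000 | D = 10,000 | D = 15,000 |
|---|---|---|---|
| 0% | 0.909 | 0.909 | 0.909 |
| 1% | 0.908 | 0.904 | 0.898 |
| 2% | 0.907 | 0.900 | 0.887 |
| 3.8% | 0.905 | 0.891 | 0.868 |

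A chance imbalance of 2 affected patients between arms moves the difference by 2D/47.6, which is 210 to 630 counts, or 4% to 13% of 5,000.

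**6. Effect on the within-arm tests.** The mean change from Week -1 rises by about p × D if activity recovers fully. At p = 1.1% to 3.8% and D = 5,000 to 15,000 this is about 60 to 560 counts, or 1% to 11% of the planned 5,000 difference.

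**The case against.** The strongest reply is that several provisions already narrow the gap.

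- **The Visit 3 check.** A reader might infer that anyone admitted during baseline stays eligible. That goes too far: the current-hospitalization part is undated and all criteria are confirmed before the IRT contact, so a patient still in hospital is excluded. This stands, but it does not reach a patient already discharged.
- **Stable therapy.** A reader might also infer that such patients must be randomized because no exclusions may be added. Section 3.6 requires confirmed stable heart failure therapy first, and SAP section 2.3.1 lists adverse event and physician decision as screening-phase outcomes. So randomization is possible, not automatic. Yet an admission that leaves heart failure drugs unchanged satisfies section 3.6, and no rule says when a baseline admission should end screening.
- **The watch rules.** If the watch was off, the baseline may be repeated or Week -2 used. This stands for watch-off stays only.
- **Screening-only criteria are ordinary here.** Exclusion 20 looks back from screening and exclusion 21 tests potassium at screening only, and section 4.2 gives representativeness as the reason for limiting exclusions. Anchoring to enrollment is thus not an error in itself. The point is narrower: hospital stay bears directly on the quantity measured in the baseline week.
- **Small effect.** Admission rate and activity drop are both assumed, and the effect on power is modest. This stands.

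**Conclusion.** The gap is real and narrow. A patient admitted and discharged wholly between Visit 1 and Visit 3 is not excluded by exclusion 6 and may be randomized. With a worn watch and at least 5 valid days, the affected Week -1 is the primary baseline.

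On the assumed rates, at most about 2 to 5 of 136 patients are involved. Power stays at about 0.89 or above with up to 2% affected; the least favourable combination shown (3.8%, 15,000 counts) gives 0.87. The sample size need not change.

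Three stronger readings are not supported:
- *That the primary comparison is biased.* The admission precedes randomization, so affected baselines are balanced in expectation. The cost is noise and chance imbalance. Upward bias arises only in the uncontrolled Week 9 and 16 changes in the sacubitril/valsartan arm.
- *That a few outlying changes would switch the primary analysis to the log scale.* A Shapiro-Wilk rejection is not enough; protocol section 9.4.2 and SAP section 2.5.2 also require the lognormal to fit better.
- *That exclusion 6 was meant to prevent early dosing after discharge.* Neither document gives a reason for it. The point rests on the validity of the baseline measurement alone.

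**What to change.** 1. **Protocol section 4.2, exclusion 6.** Extend the existing hospital-free condition to Visit 3 by adding subjects hospitalized at any time between enrollment and randomization. Allow rescreening with a new 2-week baseline once the existing 4-week condition is met again.
2. **Reconcile sections 3.6, 4.2, 5.3 and 6.6.4.** State whether stable therapy is an eligibility criterion, which conditions are re-tested at Visit 3, and whether a repeated baseline phase re-dates enrollment.
3. **SAP section 2.5.** Flag any baseline week that overlaps or follows a hospital stay begun after enrollment, and add a sensitivity analysis of the primary endpoint and the Week 9 and 16 within-arm changes without those patients. The flag is fixed before randomization, so excluding on it does not compromise the randomized comparison. SAE reporting from consent captures most admission dates; section 7.2.1 leaves some elective or social stays out, so ask about any stay at Visit 3.

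Cost: one sentence in an amendment, a short SAP addition, one question at Visit 3, and a few deferred or rescreened subjects (at most about 2 to 5 per 136 on the assumed rates). If the sponsor prefers to keep such patients for representativeness, item 3 alone would make the effect visible, though it would not protect the baseline.
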